#### **LIST OF FIGURES**

Figure 1	Study Design	8
Figure 2	Multiple Testing Procedure for Key Secondary Endpoints	.30

Abbreviation or Specialized Term	Definition	
AC	adjudication committee	
ADA	antidrug antibody(ies)	
AE	adverse event	
AESI	adverse event of special interest	
CSR	clinical study report	
CTCAE	Common Terminology Criteria for Adverse Events	
ECG	electrocardiogram	
FAS	full analysis set	
GC	glucocorticosteroids	
GCP	good clinical practice	
ICF	informed consent form	
Ig	immunoglobulin	
IgG4-RD	immunoglobulin G4-related disease	
IP	investigational product	
IV	intravenous(ly)	
OLP	Open-label period	
PT	preferred term	
RCP	randomized-controlled period	
RI	responder index	
SAE	serious adverse event	
SDAY	Study day	
SFP	Safety follow-up period	
SOC	system organ class	
TEAE	treatment-emergent adverse event	
TEAESI	treatment-emergent adverse events of special interest	
TESAE	treatment-emergent serious adverse event	
US	United States	

# LIST OF ABBREVIATIONS

## **1 INTRODUCTION**

This document describes the statistical analysis for protocol VIB0551.P3.S2, A Phase 3 Randomized, Double-blind, Multicenter, Placebo-controlled Study of Inebilizumab Efficacy and Safety in immunoglobulin G4-related disease (IgG4-RD).

# **2 STUDY OVERVIEW**

#### 2.1 Study Objectives and Endpoints

The objectives and corresponding endpoints are listed in Table 1 below:

Pr	imary objective	Endpoints/variables
•	To evaluate the efficacy of inebilizumab in reducing the risk of a disease flare in patients with IgG4-RD.	• Time to disease flare, defined as the time in days from Day 1 (dosing) to the date of the first treated and Adjudication Committee (AC)-determined IgG4-RD flare within the 52-week randomized controlled period (RCP). The date of disease flare is defined as the date of initiation of any flare treatment (new or increased glucocorticoids (GC) treatment, other immunotherapy, or interventional procedure) deemed necessary by the Investigator for the flare.
Se	condary objectives	Endpoints/variables
•	To evaluate the safety and tolerability of inebilizumab in patients with IgG4-RD.	• Incidence of treatment-emergent adverse events (TEAEs), treatment-emergent serious adverse events (TESAEs), and treatment-emergent adverse events of special interest (TEAESI) during the 52-week RCP and during the open- label period (OLP).
		• The incidence of anti-drug antibodies (ADA) directed against inebilizumab during the RCP.
•	To evaluate the effect of inebilizumab on other measures of disease activity.	• Annualized flare rate for treated and AC- determined flares during the RCP.
		• The proportion of subjects achieving flare-free, treatment-free complete remission at Week 52, defined as the lack of evident disease activity at Week 52, no AC-determined flare during the RCP, and no treatment for flare or IgG4-RD disease control except the required 8-week GC taper. Lack of evident disease activity is defined as either an IgG4-RD Responder Index (RI, Wallace) score of 0, or a determination by the investigator that no disease activity is present based on physical, laboratory, pathology or other evidence.
		• The proportion of subjects achieving flare-free, corticosteroid-free complete remission at Week 52, defined as the lack of evident disease activity at Week 52, no AC-determined flare during the RCP, and no corticosteroid treatment for flare or disease control except the required 8-week GC

Table 1	Study	Objectives	and	Endpoints
---------	-------	------------	-----	-----------

	taper. Time to initiation of first treatment (medication or procedure) for new or worsening disease activity by the Investigator within the RCP, regardless of AC determination of flare.
	• Annualized flare rate for AC-determined flares, whether or not treated, during the RCP.
	• Glucocorticoid use, calculated as the cumulative GC dose taken for the purpose of IgG4-RD disease control during the RCP.
Exploratory objectives	Endpoints/variables
Descling is defined as the last new missing valid share	

Baseline is defined as the last non-missing valid observation prior to the 1 Investigational product (IP) administration during RCP. In cases where measurements are taken on the same day as the first administration of IP and no time is reported, it will be assumed that these measurements are taken prior to the first administration of IP.

#### 2.2 Study Design

This is a multicenter, randomized, double-blind (Investigator, subject, and Sponsor will be blinded to treatment assignment), placebo-controlled, parallel-cohort study to evaluate the efficacy and safety of inebilizumab for prevention of disease flare in adults with active IgG4-RD who are at high risk of recurrent flare.

The study will be conducted at approximately 60-80 sites in 20 countries. The expected duration of each subject's participation in this study is up to 400 days (screening and RCP) or, for eligible subjects who enroll in the optional OLP, up to 2,273 days (screening, RCP, interval between RCP and OLP, and OLP). A safety follow-up period (SFP) of 2 years after the last IP dose will take place for subjects who do not enter the OLP or who discontinue IP during the OLP.

Subjects will be stratified by first or subsequent IgG4-RD manifestation (i.e., newlydiagnosed vs. recurrent) and randomized 1:1 by an interactive voice/web response system (IXRS) to one of two blinded treatment groups:

- Inebilizumab group: Subjects will receive an infusion of inebilizumab 300 mg IV on Day 1, Day 15, and at Week 26.
- Placebo group: Subjects will receive an infusion of placebo on Day 1, Day 15, and at Week 26.

During the 52-week RCP, subjects will attend monthly visits for study assessments and procedures. Suspicion of flare will trigger diagnostic assessments by the Investigator. The Investigator will determine if the event meets protocol defined criteria for flare, and, independent of the flare determination, will decide if the event requires treatment. The same data reviewed by the Investigator will also be evaluated by a central, independent, and blinded AC (blinded to treatment allocation and to investigator determination of meeting flare criteria or requiring treatment) that will determine whether protocol-defined flare criteria are met.

All subjects should be followed through the end of the RCP. A subject who decides to withdraw from the RCP should be asked to complete the final visit (early discontinuation visit [EDV]) for safety follow-up. Subjects who discontinue IP during the RCP without withdrawing from the study will remain in the RCP for its duration and complete the Day 365 visit.

In an optional 3-year OLP, all eligible subjects who choose to participate will receive inebilizumab. Subjects assigned to the placebo group during the RCP will receive 2 inebilizumab infusions (OLP Day 1 and Day 15), while those assigned to the inebilizumab group in the RCP will receive IV inebilizumab on OLP Day 1 and a placebo infusion on Day 15. Both groups will then receive inebilizumab infusions every 6 months for the duration of the OLP. The IXRS will assign the OLP Day 15 treatments, maintaining the blind for the RCP treatments.

In addition, all subjects who discontinue IP during the OLP, or who do not participate in the OLP, will be asked to return to the clinic for a series of follow-up visits with limited assessments, occurring every six months for a total of two years of SFP after their last IP administration. This SFP will provide data on recovery of B cell counts and immunoglobulin levels and monitor for safety events after the IP discontinuation.

A study schematic is presented in Figure 1.

D = day; IV = intravenous.

#### 2.3 Sample Size

A total of 39 flares are required to detect a relative reduction of 65% in risk for time from Day 1 (dosing) to onset of flare during the RCP with at least 90% power, two-sided  $\alpha = 0.05$ , and a 1:1 randomization ratio based on log-rank test for comparison. Assuming the probability of having a treated and AC-determined IgG4-RD flare during the RCP in the placebo group is 0.35 (Yunyun et al, 2017; Yunyun et al, 2019; Wang et al, 2018), a total of 160 subjects (80 subjects per treatment group) are expected to be enrolled using the following formula:

$$N = \frac{E}{\Pr\left(Fail\right)}$$

where

#### $Pr(Fail) = 0.5P_0 + 0.5P_1$

is the weighted average of the failure probabilities  $P_0$  and  $P_1$  and in the placebo and inebilizumab groups, respectively. Assuming the probability of having a treated and ACdetermined IgG4-RD flare during the RCP in the placebo group is 0.35 and an exponential survival distribution, the hazard rate for the placebo group is  $-\log(1-0.35) = 0.4308$ . With the hypothesized treatment effect of a relative reduction of 65% in risk, the hazard rate for the inebilizumab group during the RCP is  $-0.35 \log(1-0.35) = 0.1508$ . Pr(Fail) =  $(0.35 + [1 - \exp(-0.1508)])/2 = 0.245$ .

The hypothesized 65% reduction in risk is an estimate based on the observed treatment effect for attack reduction with inebilizumab in the phase 3 NMOSD trial (77% reduction in risk), and limited published clinical data on the efficacy of the B cell-depleting agent rituximab in IgG4-RD.

The first 50 subjects who complete the RCP or have a treated and AC-determined IgG4-RD flare will be randomly sampled and used to simulate different sample sizes between 160 and 200 in increments of 10. For each of the sample sizes, this simulation process will be repeated 10,000 times to give a distribution of the number of flares. The target sample size is the one that achieves 39 flares 90% of the time.

If the blinded assessment from the first 50 subjects indicates that the number of flares expected with 160 subjects is less than 39, then the sample size will be adjusted based on the above exercise to the number of subjects anticipated to achieve 39 flares with a maximum of 200 subjects (100 subjects per treatment group).

# **3** STATISTICAL METHODS

#### 3.1 General Considerations

The efficacy endpoints will be summarized at scheduled visits during RCP and OLP, respectively. For subjects in the OLP, the efficacy may also be summarized over the combined RCP and OLP to characterize the durability of the treatment effect, if applicable. And the summary over the combined RCP and OLP will be based on the subjects who received any dose of inebilizumab.

The safety endpoints will be summarized for the RCP, OLP, combined RCP and OLP, and SFP, respectively.

All efficacy analyses described below apply to the RCP unless stated otherwise.

The analyses with a treatment policy strategy will include all data captured during the 52week RCP, defined as the period after first IP administration at Visit 2 (Day 1) to the conclusion of the scheduled last RCP visit at Visit 15 (Week 52), inclusive, up to but not beyond Day 1 of the OLP.

As sensitivity analyses, the analyses applying the while-on-treatment strategy for safety endpoints will include all data captured while subjects are on treatment, defined as the period after randomization at Visit 2 and 6 months (183 days) after the last treatment during the RCP, inclusive.

All statistical calculations will be primarily performed using SAS® System Version 9.4 or higher. Tabular summaries will be presented by treatment arm. Categorical data will be summarized by the number and percentage of subjects in each category. Continuous variables will be summarized by descriptive statistics, including number of observations, mean, standard deviation, median, Q1, Q3, minimum, and maximum. Data listings will be sorted by treatment group and subject number.

Where appropriate, model-based estimates will be presented with their two-sided 95% confidence interval (CI) and p-values. Unless otherwise stated, nominal p-values will be reported and rounded to 4 decimal places.

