#### 3.3.6 Safety Follow up Analysis Set

The Safety follow up Analysis Set includes all subjects who are eligible for the SFP.

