#### **3.6.1** Adverse Events

Adverse event and serious adverse event collection begins after the subject signs the informed consent document and continues until the end of study visit. AEs and SAEs collected during the RCP will be analyzed using a treatment policy strategy (which includes all data captured during the RCP), and a while-on-treatment strategy (which includes all data captured while subjects are on treatment). AEs and SAEs collected during the OLP, SFP and combined RCP and OLP, will be analyzed using a treatment policy strategy. For subjects who withdraw from the study, data collected up until the last visit will be included. Table 5 defines TEAEs for different analyses.

RCP (Treatment Policy)	RCP (While-on- treatment)	OLP	Combined RCP and OLP (Any Inebilizumab Analysis Set)	SFP
A TEAE is defined as any AE with onset date on or after the first RCP IP dose, and on or before the end of RCP.	A TEAE is defined as any AE with onset date on or after the first RCP IP dose, and on or before 6 months (183 Days) after the last RCP dose.	A TEAE is defined as any AE with onset date on or after first OLP IP dose and up to the end of OLP (prior to the SFP entry if a subject enrolled into SFP).	A TEAE is defined as any AE with onset date on or after the first inebilizumab dose (either RCP or OLP) and up to and including the day prior to the end of RCP (if a subject didn't enroll into OLP) or the end of OLP (i.e., the day prior to the SFP entry, if a subject rolled over to OLP).	TEAE is defined as any AE with onset date after the last IP dose during the study.

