#### **Table 5 Definition of TEAEs for Different Analyses**

An adverse event of special interest (AESI) is one of scientific and/or medical interest specific to understanding safety and action of the IP. The following are considered AESIs in this study:

- Anaphylaxis and serious hypersensitivity reactions
- Infusion-related reactions (IRR)
- Immune complex disease
- Cytopenia
- Serious and/or opportunistic infections, including Progressive Multifocal Leukoencephalopathy (PML).

The AESIs (investigator reported) will be summarized by Category and PT. The risk difference and corresponding 95% CI calculated by the Miettinen and Nurminen score method in cumulative incidences of AESIs by week 52 between inebilizumab and placebo groups may be presented as appropriate. In addition, the time to first instance of an AESI and duration of the AESI will be summarized by treatment group when appropriate.

In addition, following sponsor identified AESIs will also be summarized: IRR, anaphylaxis, serious hypersensitivity reactions, immune complex disease, cytopenia, serious infections, and opportunistic infections. The detailed definition of sponsor identified AESIs will be included in the statistical programming plan (SPP).

AEs will be coded to the corresponding system organ class (SOC) and preferred terms (PT) using the most recent version of the Medical Dictionary for Regulatory Activities (MedDRA). In addition, summary of AEs and SAEs by SOC and FDA Medical Query (FMQ) will also be provided for RCP and the combined period of RCP and OLP.

The number and percentage of subjects reporting TEAEs and TESAEs will be summarized for each treatment group by SOC and PT, by severity, and by relationship to the IP. If the same AE occurs multiple times within a particular subject, the highest severity and level of relationship observed will be reported.

TEAEs and TESAEs will be summarized as described in Table 6.

TEAEs per 100 Person-years for a specific reporting period will be calculated as

$$= 100 \times \frac{\text{Total number of TEAEs for specific reporting period}}{\text{Total Person years for specific reporting period}}$$

The person-year for while-on-treatment analyses will be defined as (Date of 6 months [183 Days] after the last RCP dose - 1st RCP dose date +1)/365.25. See Table 4 for the definition of person-years for other analyses.

Overall summary of TEAEs
TEAEs by SOC and PT
TEAEs with severity $\geq$ Grade 3 by SOC and PT

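### By default, safety follow-up tables put former placebo subjects treated with inebilizumab in the open-label period in the same placebo column as never-exposed subjects; the SAP should set these columns by actual exposure.

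*SAP*

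**What the plan says.** SAP 3.1 first sets the reporting periods: "The safety endpoints will be summarized for the RCP, OLP, combined RCP and OLP, and SFP, respectively". It then gives the layout rule: "Tabular summaries will be presented by treatment arm". SAP 3.6.1 repeats the rule for adverse events, in the text below Table 5: "The number and percentage of subjects reporting TEAEs and TESAEs will be summarized for each treatment group by SOC and PT". The design section randomises subjects "to one of two blinded treatment groups" and names no other groups.

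Entry to the SFP is open to "subjects who do not enter the OLP or who discontinue IP during the OLP" (SAP 2.2). The analysis set is defined in one sentence, with no grouping rule: "The Safety follow up Analysis Set includes all subjects who are eligible for the SFP" (SAP 3.3.6).

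SAP 2.2 also states that subjects randomised to placebo receive inebilizumab once they enter the OLP. It gives the purpose of the SFP as describing B-cell and immunoglobulin recovery and monitoring safety once IP has stopped.

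**The concern.** The placebo arm in the SFP is not one population. Some subjects have had only placebo. Others have had at least one inebilizumab infusion in the OLP and have since stopped. A single placebo column would average the two, and events that follow inebilizumab would appear under placebo.

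This works against what the SFP is for. A recovery summary is informative only for subjects whose B cells or immunoglobulins could have been lowered by the drug. A background rate of infection or cytopenia is informative only if it comes from subjects who never had the drug. A mixed column gives neither, and it narrows any visible contrast with the inebilizumab column.

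**Working it through.** There is no planned figure to reproduce, because the point concerns table columns. The check is a reading of the rules together, followed by an illustration of size.

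**1. Which rule governs SFP columns?** SAP 3.1 lists the SFP among the safety periods and states the by-arm rule without exception. Treatment arm is not defined period by period. Where SAP 3.4.1 uses the term, for the curve of time to RCP discontinuation, it means the randomised arms. Read literally, the SFP columns are inebilizumab and placebo as randomised.

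**2. Who falls in each column?**

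| Randomised arm | Route to SFP | Ever had inebilizumab? | Column under the by-arm rule |
|---|---|---|---|
| Placebo | Did not enter OLP | No | Placebo |
| Placebo | Stopped IP in OLP | Yes | Placebo |
| Inebilizumab | Did not enter OLP | Yes | Inebilizumab |
| Inebilizumab | Stopped IP in OLP | Yes | Inebilizumab |

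The first two rows are the mixture. (The table assumes that subjects received their assigned treatment.)

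**3. Does another rule separate them?**
- SAP 3.3.2 groups subjects by treatment actually received, but limits this to RCP analyses.
- SAP 3.3.4 defines the Any Inebilizumab set on data from first inebilizumab onward, with no end date. SAP 3.6 then assigns that set only to the combined RCP and OLP.
- For OLP subjects, Table 5 ends the combined adverse event window on the day before SFP entry. Events in the SFP fall outside it.
- Table 2 re-anchors baseline and Day 1 to first inebilizumab for the combined RCP and OLP. Its SFP column does not: baseline precedes the first RCP infusion for everyone, and Day 1 follows the last IP of either kind.
- Protocol 9.5.5 assigns data after inebilizumab to the Any Inebilizumab set, without limiting the period. The SAP does not apply this to the SFP.

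No visible SAP rule separates the first two rows.

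**4. How large could the mixture be?** The planned 80 placebo subjects come from SAP 2.3. OLP entry *e* and the proportion stopping IP in the OLP *s* are assumptions; the documents give neither.

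Never exposed = 80 × (1 − e). Exposed = 80 × e × s. Exposed share f = exposed / (exposed + never exposed).

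| e | s | Never exposed | Exposed | f |
|---|---|---|---|---|
| 0.80 | 0.10 | 16 | 6.4 | 6.4/22.4 = 29% |
| 0.90 | 0.15 | 8 | 10.8 | 10.8/18.8 = 57% |
| 0.90 | 0.30 | 8 | 21.6 | 21.6/29.6 = 73% |

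**5. What would that do to an event rate?** Assume, for illustration only, a risk of 5% in never-exposed subjects and 10% in exposed subjects, with the inebilizumab column also at 10%. Placebo column rate = (1 − f) × 5% + f × 10%. Share of placebo-column events from exposed subjects = f × 10% / column rate.

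| f | Placebo column | Apparent difference (true: 5 points) | Placebo-column events from exposed subjects |
|---|---|---|---|
| 25% | 6.25% | 3.75 | 40% |
| 50% | 7.5% | 2.5 | 67% |
| 75% | 8.75% | 1.25 | 86% |

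Whenever the exposed risk is higher, the difference shrinks towards zero.

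**The case against.** A reader might infer that the plan deliberately credits inebilizumab events to placebo. The documents do not support that. No sentence says that SFP columns are the randomised arms. The by-arm sentence is a general formatting rule, and arm could be read as a treatment sequence: the protocol's account of the earlier NMOSD study labels open-label subjects that way (protocol 2.1.5.3). Protocol 9.5.5 points towards reporting by exposure. All of this stands. It makes the problem a default left in place and a misalignment between protocol and SAP, not a stated intention.

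A reader might also lean on SAP 3.6.1: "AEs and SAEs collected during the OLP, SFP and combined RCP and OLP, will be analyzed using a treatment policy strategy". In this SAP, treatment policy determines which data are included, not which column a subject belongs to. It adds nothing to the column argument.

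Three further limits stand:
- The visible SAP contains no B-cell table specification, and some text is blacked out, so the grouping of B-cell results may be settled there. The adverse event argument does not depend on it.
- No between-group SFP test is visible. The risk difference for events of special interest is set at Week 52, and all treatment-emergent events are listed, so individual cases remain traceable.
- The entry rates, stopping rates and event risks used above are assumptions.

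None of this supplies the missing column definition. Someone programming the SFP tables from the SAP would have only the by-arm rule to follow.

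**Conclusion.** The point holds as a gap with an unhelpful default. Followed literally, the SAP pools never-exposed and OLP-exposed former placebo subjects in one SFP placebo column, and the exposure-based intent of protocol 9.5.5 is lost at SFP entry. The mixing follows from the rules alone, provided that both kinds of subject enter the SFP. Its size does not: the 29% to 73% range rests on assumed OLP entry and discontinuation, and the diluted differences rest on assumed risks as well. Only SFP safety summaries are affected. The primary, key secondary and RCP safety analyses are not. This is a cheap improvement rather than a threat to the trial's conclusions.

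**What to change.** In SAP 3.3.6 and 3.6, state that SFP adverse event and immunoglobulin tables are presented by actual inebilizumab exposure. Apply the same to B-cell tables if text not shown does not already do so. The minimum is two columns, never versus ever exposed. Where numbers allow, split ever exposed by whether the last inebilizumab dose fell in the RCP or the OLP. The last-dose-in-OLP column would still combine subjects first treated in the RCP with those first treated in the OLP, whose cumulative exposure differs; a footnote giving the counts would make that visible. Align the wording with protocol 9.5.5.

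The cost is SAP text and table shells, using dosing data already collected. The drawback is smaller columns. Making the change before any SFP table is produced avoids choosing the columns after seeing the data.
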